Appendix A: Orientation Script	
Appendix B: Pilot Testing Survey	
Appendix C: Goal Attainment Tool	
Appendix D: Self-Efficacy Tool	

1.0 BACKGROUND

In contrast with other major chronic conditions such as heart disease and stroke, cancer care does not routinely integrate evidence-based rehabilitation services within the standard continuum. This protocol describes a structured process for the development, implementation, and preliminary evaluation of a novel, integrated rehabilitation intervention for survivors of head and neck cancer (HNC) called the Rehabilitation Consultation (RC). The RC program goals are to increase knowledge about rehabilitation needs and resources to meet those needs; to establish individualized rehabilitation goals for HNC survivors and personalized action plans to meet those goals; and to provide support to HNC survivors for the implementation and evaluation of action plans. The goals will be personally important to the individual survivor, and the action plans will be achievable, using resources they can access close to home rather than at the cancer centre, when possible. Additionally, the RC will be integrated into routine HNC follow-up procedures, and will be administered as soon as possible following active cancer treatment. It will be led by a professional with a background in one of the traditional rehabilitation professions, and will include the following 3 components: 1. A brief, HNC-specific functional evaluation; 2. A resource compendium; 3. Collaborative goal-setting, action-planning, and follow-up processes.

Reductions in function and quality of life are particularly high in HNC, as the disease and treatment cause more diverse and serious impairments than many other cancers. Issues include reductions in swallowing, speech, neck and upper extremity mobility, general deconditioning, fatigue, insomnia, lymphedema, neuropathies, visible facial deformity, and psychological distress [1-9]. In addition, a range of more global functional issues result, including body image dissatisfaction, cognitive and behavioural problems [10], decreased role functioning [11], decreased nutritional status [12], decreased communication [5], poor driving performance [13] and inability to return to work [14,15]. Among the 9000 new cases of HNC in Canada each year [16], an increasing proportion is among young, working-

Development and pilot evaluation of rehabilitation consult for survivors of head and neck cancer

aged patients, primarily related to the ongoing epidemic of oropharyngeal cancer associated with Human Papillomavirus [17]. Without rehabilitation services, the influx of younger survivors may increase the societal burden of the illness through loss of employment, increased absenteeism, and the financial, social, and potentially emotional effects on their families which may include young dependents [18,19].

Cancer rehabilitation has been defined as coordinated, professional care designed to enable people to maximize physical, social and psychological function within the limits imposed by the disease and treatment effects, and to engage in personally valued activities within their social contexts [20].

Rehabilitation interventions for HNC are demonstrably safe, feasible, cost-effective, and associated with improvements in quality of life, general conditioning, swallowing, muscle function, insomnia, pain, weakness, anorexia, shortness of breath, tube-feeding dependency, hospital readmissions, depression and distress [7,21-25]. Although evidence exists to support cancer rehabilitation, services are fragmented. Rehabilitation professionals are consulted infrequently and often long after treatment ends, when chronicity of problems limits the impact of intervention [unpublished observations].

Additional barriers to accessing rehabilitation services include cost, issues between and among patients, oncology professionals and rehabilitation experts related to communication and awareness of available resources [unpublished observations]. There are clear potential benefits to a comprehensive, integrated rehabilitation consultation process that targets all HNC patients soon after primary cancer treatment is completed, improves communication among stakeholders, and provides linkages to appropriate resources. Therefore, the overall objective of this project is to develop, implement, and conduct a pilot evaluation of the RC. This current protocol is concerned with pre-testing of an alpha version of the RC and subsequent pilot testing of a beta version.

2.0 METHODS/DESIGN

This project employs Intervention Mapping as an ecologically valid, structured framework to develop, implement, and evaluate the RC [26]. Intervention Mapping consists of 6 steps: 1. Needs assessment 2. Definition of program objectives 3. Selection of theory-based intervention methods 4. Production and pretesting 5. Adoption, implementation, and sustainability planning 6. Process and effect evaluation. Research staff and the investigators will oversee the project with input from an eight-member Advisory Panel, including patient and family representatives, health care professionals working in oncology, health care professionals working in rehabilitation, and representatives of the provincial cancer care system. All Intervention Mapping steps are described below. **Note that Steps 1 -4 have previously been completed or are in progress (REB # 13-6877-CE), with Steps 5-6 planned and the subject of this current proposal.**

2.1 Step 1, Needs Assessment

In the previously-completed Step 1, *Needs Assessment*, we used information gleaned from focus groups with patients, family members, and front-line health care professionals (unpublished data, manuscript under preparation) and from a scoping literature review (unpublished data, 1 manuscript submitted, 1 manuscript under preparation) to establish the rehabilitation needs of HNC survivors. The rehabilitation needs appear as Phase 2 and Phase 1 in Table 1. We next identified highly relevant and modifiable behavioural and environmental factors that contributed to the identified issues (Phase 3, Table 1), their determinants (Phase 4, Table 1), and the items targeted for change with the RC intervention (items in italics in Table 1). Finally, the following RC program goals were developed: 1. Increase knowledge of all stakeholders about rehabilitation needs and about resources to meet those needs; 2. Establish individualized rehabilitation goals and personalized action plans for HNC survivors; 3. Provide support for the implementation and evaluation of action plans; 4. Facilitate HNC survivors' access to rehabilitation professionals where it is most feasible for them.

2.2 Step 2, Definition of Program Objectives

In the previously completed Step 2, ***Definition of Program Objectives***, the resource requirements that will enable achievement of the program goals described above were specified. The specific resource requirements to be developed as components of the RC include a brief, HNC-specific functional evaluation, an online resource compendium that includes comprehensive information about rehabilitation services in Toronto and adjacent regions as well as educational modules for specific home-based exercises, a goal-setting and action planning process, and a follow-up process. The specific behavioural requirements are that the HNC survivors be confident in goal-setting and action planning, and that all stakeholders be knowledgeable about HNC rehabilitation needs and applicable resources.

2.3 Step 3, Selection of Theory-Based Intervention Methods and Practical Applications

In Step 3, ***Selection of Theory-Based Intervention Methods and Practical Applications***, the research team reviewed the work completed in Intervention Mapping Steps 1 and 2 with the Advisory Panel. Then, the research team selected behavioural change methods from the Intervention Mapping tables [26, p 357-358] that are congruent with self-management and goal-setting theories and with the RC program parameters. Additional behavioural change methods derived from the Cognitive Orientation to daily Occupational Performance (CO-OP) approach were also incorporated, specifically cognitive strategy training and guided discovery. (Polatajko & Mandich, 2004) Behavioural change methods were linked to specific change objectives and determinants. Two members of the research team (SM and CD) then identified practical applications (such as worksheets, pamphlets, websites, videos) to enact those methods. The Advisory Panel will conduct a final review of all methods and practical applications selected in Step 3 to ensure that they mesh with the program goals and resource requirements identified in Intervention Mapping Steps 1 and 2, and will make recommendations for modifications if necessary.

2.4 Step 4: Production of Program Components and Pre Testing

Figure 1 provides the expected timeline for completion of Steps 4 through 6. In Step 4, ***Production of Program Components and Pre Testing***, all components of the RC will be developed and pre-tested for

Development and pilot evaluation of rehabilitation consult for survivors of head and neck cancer

acceptability and feasibility. The program components to be developed are as follows: a brief, HNC-specific functional evaluation; a resource compendium; collaborative goal-setting, action-planning, and follow-up processes.

The **brief HNC-specific functional evaluation** has the objectives of estimating both performance-based issues, such as swallowing or joint mobility, but also patient-determined functional and life participation issues, such as return to work or family and social role functioning. Items will be derived from the Needs Assessment completed in Step 1. The investigators and study staff will generate an initial list of items that will be reviewed for content, length, and intelligibility by the Advisory Panel, and modified as necessary.

Development of the **resource compendium** is currently underway using interviews with key informants. This piece of the RC development was initiated as part of the previously approved project (REB # 13-6877-CE). The resource compendium includes listings of rehabilitation services available in Toronto and adjoining regions that commonly refer to Toronto regional cancer centres, educational resources for patients and therapists, and materials to support the RC process, such as worksheets and pamphlets. All materials will be available online at www.hncrehab.ca and printed hard copies of materials will also be available for those survivors who have difficulty accessing the Internet.

A preliminary version of the **collaborative goal setting, action planning, and follow up processes** has been developed. All survivor/professional processes are designed to establish a strong therapeutic alliance, to engage and motivate the survivor, and to foster independence and self-management. The alpha-RC face-to-face phase (collaborative goal setting and action planning process) includes the following steps:

- A. A brief presentation (Appendix A) is given by the rehab consultant to **orient** the survivor to the reason for the consultation and the process.
- B. The rehab consultant implements the brief HNC-specific functional evaluation, and then **consults** with the survivor regarding the results. The survivor identifies the issues that are currently most important to him or her.
- C. The survivor and the rehab consultant work collaboratively to set **goals** based on issues identified by the survivor as most important to him or her. The rehab consultant teaches the survivor a global problem solving strategy, Goal-Plan-Do-Check (Meichenbaum, 1971).
- D. Using the Goal-Plan phases of the problem solving strategy, the rehab consultant and the survivor develop an action **plan** to meet the identified goals. The rehab consultant uses motivational interviewing techniques (eliciting change talk, evoking motivation to make positive changes (Miller & Rollnick, 1991) and guided discovery techniques (ask don't tell, coach don't adjust, make it obvious, and one thing at a time (Polatajko & Mandich, 2004)). Also as part of the planning process, the rehab consultant and the survivor discuss potential barriers to implementing the action plan and develop coping responses, using planning coping responses techniques (Marlatt & Donovan, 2005). The rehab consultant introduces the survivor to the resource compendium for future use, and facilitates the assembly of resources necessary to implement the survivor's plans.
- E. Telephone follow-up appointment is scheduled for between 2 and 10 weeks later, at a mutually convenient time. The survivor also has the option of attending a follow up session in person. Preferred communication strategies are set in place, and the survivor is encouraged to **execute (do)** his or her plan.

The alpha-RC telephone follow-up process includes the following steps:

- A. An email/text/or telephone reminder (as preferred by the survivor) regarding the follow-up appointment is sent 24 hours in advance.
- B. The rehab consultant phones at the designated date and time and confirms with the survivor that the appointment is still convenient.
- C. The rehab consultant re-orientes the survivor to the RC process.
- D. The rehab consultant and the survivor begin the *check* phase of goal-plan-do-check. They review the goals and the actions plans, and proceed with a discussion about the do-check portion of the problem solving strategy. The rehab consultant guides the discussion using motivational interviewing and guided discovery techniques. If the plan was successfully implemented and the goals are achieved, next steps are discussed. If the plan was not implemented or the goals were not achieved, the rehab consultant will guide the survivor to modify the plan as necessary. The rehab consultant and the survivor discuss potential barriers to implementing the newly modified action plan and develop coping responses, using techniques for planning coping responses.
- E. The need for a second follow-up appointment is discussed and, if necessary, scheduled at a mutually convenient time. If the survivor seems to be struggling, a face-to-face follow-up might be scheduled. If a follow-up is deemed unnecessary at this time, the survivor is provided with information about how to access the rehab consultant in the future, should the need arise, and discharge occurs. The rehab consultant arranges a time for the research assistant to conduct a re-assessment of the outcome measures (Research Assessment 2), as well as a semi-structured interview for participant feedback.

2.4.1 Pre Testing

2.4.1.1 Participants and Recruitment Pretesting of the alpha-RC process will be conducted using an iterative single case series of 5 to 10 survivors of HNC. Participants will be recruited from the HNC clinics at Sunnybrook Odette Cancer Centre and Princess Margaret Cancer Centre. Eligibility criterion

Development and pilot evaluation of rehabilitation consult for survivors of head and neck cancer

are adult survivors of HNC who have completed active treatment (surgery, radiation, chemotherapy or any combination thereof) within the last year. Exclusion criteria are lack of English fluency, cognitive impairment, or concurrent major degenerative conditions likely to cause functional deterioration. Two members of the research team who are radiation oncologists (IP, Sunnybrook, and JR, Princess Margaret) will review patients scheduled for follow-up at their respective HNC clinics for eligibility, and will approach those who are eligible to ask if they are interested in learning more about a rehabilitation research project. Those who express interest will be connected with an on-site research assistant, who will provide the potential participant with additional information about the study and to answer any questions they may have. If the survivor is willing, the research assistant will obtain informed consent and schedule an assessment and alpha RC intervention time. The research assistant will provide the participant with the Brief Rehabilitation Assessment for Head and Neck Cancer Survivors (BRASH) for the patient to review and complete prior to meeting with the Rehabilitation Consultant. We anticipate that we will be able to recruit 1 participant per week.

2.4.1.2 Procedures. Participants will be required to attend 3-4 sessions that are a combination of face-to-face visits and telephone calls. Session 1: Face-to-face, at the research site (either Sunnybrook or Princess Margaret) a research assistant will conduct a pre-intervention *research* assessment (approximately 60 minutes) and then on the same day, a rehabilitation consultant, licensed physiotherapist [name], will administer the face-to-face phase of alpha-RC *intervention* (approximately 90 minutes). Session 2: As a second phase of the alpha-RC *intervention* process, the rehabilitation consultant (CD) will conduct a telephone follow-up with the participant (45 to 60 minutes). Session 3: Within one week of Session 2, the participant will complete a post-intervention *research* assessment with the research assistant (approximately 60 minutes), either as a face-to-face visit at the research site, or as a telephone interview. For Session 3, it will be the participant's choice to have either a face-to-face or telephone interview, based on what is most convenient for him or her. This

choice has been put in place because many patients travel to Sunnybrook and Princess Margaret from out-of-region to receive specialized treatment for head and neck cancer, making an additional face-to-face visit very inconvenient for some. It is possible that, as part of the alpha-RC *intervention*, participants will require a second follow-up session that may occur as a second telephone call or a second face-to-face meeting. This is expected to happen rarely. The rehabilitation consultant will log any additional follow-up meetings, including type (phone or face-to-face), reason for meeting, outcome of meeting, next steps.

Participants will be remunerated \$25 for each *research* visit to the site to offset their transportation and parking costs, for a total of \$50 per participant. Additional *intervention-only* visits will not have any remuneration.

At both the pre and post intervention research assessments, the following constructs will be evaluated: function, quality of life, self-efficacy, community participation, goal attainment, and return to work status (if applicable). Additionally, the research assistant will collect data on the time to complete the assessment battery; perceived respondent burden; and ease of use of all tools. At the post-intervention assessment, the participant will be asked to complete a survey related to the content and process of the alpha-RC. Table 2 describes all tools to be used. The rehabilitation consultant (CD) will video record the face-to-face phase and audio record the follow-up telephone call so that the processes can be reviewed and analysed in depth. The following information will be extracted from these recordings: time required for each segment in the process; adherence to planned methods and theory; challenges and successes with each participant.

Descriptive analysis will be conducted; the research team will review results, and then make decisions about adaptations to the alpha-RC and finalization of the outcome measure battery. The alpha-RC will

be modified iteratively based on the information gleaned from each survivor, outcome data, and feedback from research team members. Step 4 will be considered complete when the investigators are satisfied that a version of the RC suitable for formal pilot evaluation has been developed, the beta-RC.

2.5 Step 5: Planning for adoption, implementation, and sustainability.

This is a planning step, in which a logic model will be developed to guide the initial implementation and program evaluation. Specific objectives for adoption, implementation, and sustainability will be established, and determinants of those will be considered. We will seek input on the logic model from the Advisory Panel.

As stated in sections 2.1 and 2.2, two of the objectives of the overall study are: 1. Increase knowledge of all stakeholders about rehabilitation needs and about resources to meet those needs; 2. Facilitate HNC survivors' access to rehabilitation professionals where it is most feasible for them. To assist in this stage, head and neck cancer patients will be surveyed in clinic to determine their baseline level of awareness of rehabilitation services, where they receive any current information, and their preferences for receiving this information. Any consenting head and neck cancer patient will be eligible for the survey, but only those who meet inclusion criteria for the rest of the study will be approached for participation in the rehabilitation consult. We anticipate surveying 20-30 patients. This information will provide input into the design of adoption and implementation strategies to address the above objectives, and plan for long term sustainability. The same survey will be administered in clinic, to a separate sample of 20-30 patients, after these strategies have been implemented.

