Self-Efficacy	HNC RC Self-Efficacy Tool	There was no existing tool which adequately measured self-efficacy as it relates to the goals of this study. Therefore, a self-efficacy tool was created, using a 0-100 rating scale, based on Bandura (2006) "Guide to Constructing Self-Efficacy Tools" to measure the confidence of participants to achieve outcomes specific to this study. This tool is included as Appendix D.
Return to Work	Radiation Therapy Oncology Group (RTOG) Work Status Questionnaire [47]	The RTOG Work Status Questionnaire is a brief, patient-report tool that takes less than 5 minutes to complete. It was designed for use in RTOG trials, and psychometric properties have not been tested, but meets content validity criteria and sensibility criteria.
Goal Attainment	Goal Attainment Tool	Participants are asked about how well they currently perform a stated goal, which they develop in consultation with the rehabilitation consultant, how satisfied they are with this performance, and their confidence they can do the goal, and rate these on a scale of 0-100. A score of 0 represents low performance/satisfaction, and 100 represents the highest level of performance/satisfaction. This tool is included as Appendix C.
Patient Perspective Intervention Process	Rehab Consult Process Survey	Items for this survey were derived from questions posed in interview format during an earlier testing phase. 17 statements are scored using a 3-point Likert-type scale. Statements concerns intervention process issues such as timing, ease of use, and value of specific consult segments. This can be found in Appendix B.

Table 3: Pilot (beta) testing version of Rehabilitation Consult Process

Name	Process Steps	Methods
Orientation	A. A brief orientation (Appendix A) is given by the rehab consultant to orient the survivor to the reason for the consultation and the process.	Advance Organizer
Consultation	B. The rehab consultant reviews the brief HNC-specific functional evaluation (BRASH), and then consults with the survivor regarding the results. The survivor identifies the issues that are currently most important to him or her. If the participant has no goals, the rehabilitation closes the session by reinforcing that the options available if he/she has issues arising at a later time, and providing information on accessing the resource compendium.	Goal-setting Individualization Therapeutic alliance Facilitation Participatory problem solving

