Goal-setting	C. The survivor and the rehab consultant work collaboratively to make goal statements based on issues identified by the survivor as most important to him or her. The rehab consultant administers a goal attainment tool (Appendix D) wherein the participant rates his or her current performance, satisfaction, and confidence with the goals.	Goal-setting Individualization Therapeutic alliance Facilitation Participatory problem solving Cognitive strategy training
Teach cognitive strategy	D. The rehab consultant teaches the global problem solving strategy, Goal-Plan-Do-Check (Meichenbaum, 1971).	
Action Planning, Planning Coping Responses, and Introduction to Resources	E. Using the Goal-Plan phases of the problem solving strategy, the rehab consultant and the survivor develop an action plan to meet the identified goals. The rehab consultant uses motivational interviewing techniques (eliciting change talk, evoking motivation to make positive changes (Miller & Rollnick, 1991) and guided	Individualization Therapeutic alliance Facilitation Participatory problem solving Motivational interviewing techniques Framing Guided discovery Implementation intentions Planning coping responses

	
discovery techniques (ask don't tell, coach don't adjust, make it obvious, and one thing at a time (Polatajko & Mandich, 2004)). The rehab consultant reviews the rehabilitation resources of which the survivor may already be aware, or accessing. The rehab consultant reviews the study website (resource compendium) (www.hncrehab.ca), with the survivor, for future use, and facilitates the assembly of resources previously unknown to the survivor, which are necessary to implement the survivor's plans. Also as part of the planning process, the survivor identifies potential barriers to implementing the action plan and develops coping responses, using planning coping responses techniques (Marlatt & Donovan, 2005), all facilitated by the rehabilitation consultant.
	Verbal persuasion
Execution	
F. Facilitated by the rehab consultant, the survivor reviews his or her goals and action plan for clarity, and is encouraged to execute (do) his or her plan. Follow-up appointment is scheduled for between 2 and 10 weeks later, at a mutually convenient time. This may be in person, or via telephone, as per survivor's preference.
	Implementation intentions Planning coping responses
Follow-Up Process		

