Reminder	
A. A telephone reminder regarding the follow-up appointment is made 24 hours in advance.
	Advance organizer Individualization
Re-Orientation	
B. The rehab consultant phones at the designated date and time and confirms with the survivor that the appointment is still convenient. The rehab consultant re-orient the survivor to the RC process.
	Facilitation Individualization
Checking	
C. The rehab consultant and the survivor begin the check phase of goal-plan-do-check. They review the goals and the rehab consultant
	Self monitoring of behavior Individualization Goal setting Motivational interviewing

	
re-administers the goal attainment tool. Subsequently, the actions plans are reviewed and they proceed with a discussion about the do-check portion of the problem solving strategy. The rehab consultant guides the discussion using motivational interviewing and guided discovery techniques. If the plan was successfully implemented and the goals are achieved, next steps are discussed. If the plan was not implemented or the goals were not achieved, the rehab consultant will guide the survivor to modify the plan as necessary. The rehab consultant and the survivor discuss potential barriers to implementing the newly modified action plan and develop coping responses, using techniques for planning coping responses.
	
techniques Self monitoring of behaviours Self re-evaluation Goal setting Implementation intentions Planning coping responses Guided discovery Verbal persuasion

Discharge or Further Follow-up
	
D. The need for a second follow-up appointment is discussed and, if necessary, scheduled at a mutually convenient time. If the survivor seems to be struggling, a face-to-face follow-up might be scheduled. If a follow-up is deemed unnecessary at this time, the survivor is provided with information about how to access the rehab consultant in the future, should the need arise, and discharge occurs.
	
Individualization Facilitation Guided discovery Verbal persuasion Implementation intentions Planning coping responses

Figure 1: Timeline

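### Is the goal-attainment effect size left without a baseline because the tool is scheduled before any goal has been set?

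*Combined protocol and SAP*

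**What the plan says.** Section 2.4.1.2 sets the order of Session 1. The research assistant's assessment comes first ("approximately 60 minutes) and then on the same day, a rehabilitation consultant" then delivers the face-to-face phase). The same section lists what is measured: "At both the pre and post intervention research assessments, the following constructs will be evaluated: function, quality of life, self-efficacy, community participation, goal attainment", together with return-to-work status.

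Table 2 describes the Goal Attainment Tool: "Participants are asked about how well they currently perform a stated goal, which they develop in consultation with the rehabilitation consultant". Performance, satisfaction and confidence are each rated from 0 to 100.

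The alpha version of the consultation (section 2.4, step C) sets goals and then moves on: "The rehab consultant teaches the survivor a global problem solving strategy". It lists no goal rating. The beta version, used in Step 6, does. Table 3, step C: "The rehab consultant administers a goal attainment tool (Appendix D) wherein the participant rates his or her current performance, satisfaction, and confidence". At the follow-up contact the consultant "re-administers the goal attainment tool. Subsequently, the actions plans are reviewed and they proceed" to discuss progress. A participant without goals leaves earlier, at step B: "If the participant has no goals, the rehabilitation closes the session".

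Section 2.6 applies the 2.4.1.2 procedures to Step 6 with three listed changes: an added Session 4, the Table 3 intervention, and fidelity review with a survey. It plans exploratory, descriptive analysis with an effect size for every outcome, to inform a later controlled trial.

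**The concern.** A change score needs a first measurement, and the only research assessment scheduled before the intervention takes place when there is nothing to rate. None of the three changes in section 2.6 amends the list of constructs, so the conflict passes into Step 6.

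The Table 3 rating fills the hole but raises questions of its own. The treating consultant elicits it, whereas the research assistant collects the later research ratings. Three later ratings could be set against it, and section 2.6 does not say which one yields the effect size. It does not say how participants without goals are counted. Table 3 also points to Appendix D for the tool, while the contents list and Table 2 place it in Appendix C; Appendix D is the Self-Efficacy Tool.

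At stake would be a goal-attainment effect size that depends on an unstated choice and is then used to select outcomes and size the controlled trial.

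**Working it through.** The plan states no figure to reproduce: the sample of about 35 is a convenience number with no power calculation behind it. The check is a reading of the schedule, plus the addition of the stated windows.

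**Step 1. Which ratings precede the action plan?**

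| Occasion | Goal already stated? | Rating available |
|---|---|---|
| Pre-intervention research assessment (2.4.1.2) | No | 0 |
| Alpha consultation steps (2.4) | Yes, but no rating listed | 0 |
| Beta consultation, Table 3 step C | Yes | 1 |

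The functional evaluation that participants complete before meeting the consultant does not alter the first row. It covers functional issues; the goal statements come afterwards. Step 6 therefore has exactly one candidate baseline. It precedes step D (strategy) and step E (action plan), so it is a proper pre-plan measurement.

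**Step 2. Which ratings come later, and when?** Time is counted from Session 1. I assume a single intervention follow-up (section 2.4.1.2 expects a second one rarely) and 4.35 weeks per month.

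- Check session, consultant: "Follow-up appointment is scheduled for between 2 and 10 weeks later", so 2 to 10 weeks.
- Session 3, assistant, within one week of the check session: 2 + 0 = 2 to 10 + 1 = 11 weeks.
- Session 4, assistant, 1-2 months after Session 3: 2 + 4.35 = 6.35 to 11 + 8.70 = 19.7 weeks. That goal attainment is included here is an inference from the Session 4 battery being based on Table 2.

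One baseline and three later ratings give 1 × 3 = 3 possible changes: one with the same collector (check session) and two with a change of collector (Sessions 3 and 4).

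**Step 3. Are the three on an equal footing?** The documents rank them.

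- Section 2.4.1.2 separates research contacts from intervention contacts throughout. The check session is an intervention contact, and its rating serves the discussion of progress.
- Section 2.4.1.2 labels Session 3 the post-intervention research assessment. The last step of the follow-up process in section 2.4 describes that contact as the re-assessment of the outcome measures.
- Section 2.6, change (a), calls Session 4 a follow-up assessment.

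The natural contrast is step C to Session 3, with step C to Session 4 as the later time point. In an exploratory analysis with no hypothesis test, reporting both is legitimate. The choice between Sessions 3 and 4 is open in the same way for every outcome, so it is not a defect of this one.

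**Step 4. Denominator.** The session closes at step B for a participant without goals, before the tool is used, so that person has no score. The number rated is at most about 35 less those without goals; the documents do not give that share. Any individualised goal measure is conditional in this way.

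**Step 5. Change of collector.** The tool is the participant's own 0-100 rating. The documents support neither a size nor a direction for any collector effect, so no shift in Cohen's *d* can be derived.

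**Step 6. Pre-testing.** The alpha stage has no listed pre-plan goal rating. It involves 5 to 10 participants, is analysed descriptively and has no planned effect size. Section 2.4.1.2 also leaves the outcome battery to be finalised after it.

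**The case for a change.** The strongest argument for a change is that the remedy is only wording, and that a study meant to supply planning figures should say which two numbers it subtracts. Section 2.6 promises effect sizes for all outcomes, Table 2 counts goal attainment among them, and the results are to help define the outcomes and sample size of the next trial. Session labels do not fully settle the matter: the before half of the scheduled before-and-after pair still cannot be collected, and a consultant's re-rating and a fourth session have been added without comment.

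Two things stand. The list in section 2.4.1.2 conflicts with the order of Session 1 and with Table 2, and the appendix reference in Table 3 is wrong. An author revising the text for other reasons could tidy both.

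The inference that the effect size is therefore at risk does not stand. A team following Table 3 collects the right baseline at the right moment, and the session labels lead an analyst to Session 3 and then Session 4. A written form for the step C rating, or a log of collector and mode, would be a preference: the change of collector would remain, and nothing shows that it matters.

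**Conclusion.** The inconsistency is real but has no demonstrated consequence, so no change to the plan is needed. In Step 6 the baseline exists (Table 3, step C), the post measure is labelled (Session 3, about 2-11 weeks) and the later follow-up is labelled (Session 4, about 6-20 weeks). Stating the pairing and reporting the number rated are details that analysts supply in the ordinary course of reporting. The Appendix D reference is a clerical slip; the tool's title and the contents list identify the correct form.

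Importance is low. Section 2.6 frames the pilot's aim as the impact on function and quality of life, names no primary outcome and plans descriptive analysis only; goal attainment is one of several measures.

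The conclusion assumes that Step 6 is run as Table 3 describes, that a second intervention follow-up is rare, and that Session 4 includes the goal tool. If it does not, the Session 3 contrast is unaffected. The text of the appendices and the Step 5 evaluation plan were not available; they might settle the pairing explicitly, but the conclusion does not depend on them.
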